Epifluorescence microscopy (Leica DM4000) will be sufficient for identifying and measuring Pan NaV-immunoreactive nodes of Ranvier, length of sections for density calculations, as well as other cutaneous structures. Internodal length will be measured three dimensionally (Metamorph) in confocal-acquired images (Leica LSM510). Quantitative morphometric parameters of dermal myelinated fibers include Meissner corpuscle density (receptors per mm²), the density of their myelinated afferents (fibers per mm², axon diameter (µm), and further characterization of myelin structure in regards to internodal, nodal and paranodal length (µm) will also be calculated. Based on morphologic analyses, additional measures unique to dermal myelinated fibers may be generated and ROC curves developed to determine sensitivity and specificity. Confocal microscopy will be utilized in 3 patients at each site to confirm nodal measurements, myelinated fiber density, and confirm presence of segmental demyelination. Correlation of confocal measurements with florescence measurements will be evaluated to determine whether florescence is sufficient for accurate measurements. The PI and [name] will be analyzing the samples in a blinded fashion, and will train lab technicians in this technique which [name] and [name] have published.

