Analysis of segmental demyelination: Measurement of myelinated fiber density from glabrous skin biopsies will be calculated according to methods of previous publication (7, 23, 24). Meissner corpuscle density will also be performed for comparison. Number of papillary, dermal internodes will be calculated. Analysis of nodes of Ranvier will include quantitation of nodes with greater width (> 6 µm; (25)); branching at nodes, localization of ion channels within nodes will be quantified from 25 nodes from each biopsy, using at least 3 sections to ensure random distribution. Given the previous normal healthy control data demonstrating a 5% rate for healthy controls and 7.7% in diabetic subjects, 20% will be used as the cutoff for CIDP. 15.7% was the 95th percentile observed in both diabetic and healthy controls, with one diabetic subject having a 15% demyelination rate. Given that [name] observe demyelination in multiple fibers from previous CIDP patients sampled, we believe this will ensure diagnostic efficiency with sufficient sensitivity (9). It is unknown what treatment effects we will find, but given the standard deviation was 4.1% in the previous study, we would expect a change greater than 5% to be meaningful.

Further characterization of nodal and internodal integrity for aim 1 will be investigated with nodal staining using pan-sodium channels (7), the paranodal staining of Contactin-associated protein (Caspr; Neuromab) and internodes will be labeled by staining for myelin basic protein (MBP). These will be helpful to further measure nodal width and alsoand to evaluate for decompartmentalization of ion channels which channels, which could contribute to conduction block. An internode will be defined as a segment with intact MBP, Pan-Na and PGP9.5 staining demonstrating a node on each end. A total number of nodes per biopsy (in 4 sections) will be calculated. We will estimate segmental demyelination percentage by calculating numbers of fibers with demyelination (identified as gaps of MBP stain within a fiber where MBP stain is visible on both sides of gap and PGP 9.5 stain is present confirming axonal integrity)/total number of fibers counted (25). Repeated measures for each patient will be calculated to determine if there is decrease in segmental demyelination over time after treatment.

IVIg infusions:

Protocol Version #8:

9

Protocol Date:

10/04/2022

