10.0 Statistical Considerations

As this is a pilot study and has never been performed in this population, a formal power calculation has not been performed. A sample of 10 CIDP patients was deemed appropriate to determine if abnormal dermal myelinated pathology exists which can be evaluated in further studies. It is possible patients may have insufficient pathology. This study will provide data for future studies and will enable power calculations. Morphometric analysis of IENF, myelin thickness, intermodal length, etc will be compared using nonparametric Wilcoxon test of means of CIDP patients and healthy controls collected from previous study (18).

The data collected from Aim 1 will also be used for both Aims 2 and 3. The primary outcome measures for segmental demyelination obtained from biopsy will include the number of fibers with segmental demyelination (out of a random sample of 25 fibers), the average length of demyelinated segments, and the number of fibers with sodium channel spreading over denuded axons. As a secondary outcome, clinical outcomes such as MRC scores from the routine standard of care will be also collected.

For Aim 2, signed rank tests will be used to test whether there would be any improvement after treatment in the primary outcomes measured at 3 months and 6 months separately, compared to those measured at the baseline. Also, the outcome measures obtained from confocal vs. fluorescence alone will be compared to examine whether the measurements are similar using a random-effects model along with application of bioequivalence testing methodology.

For Aim 3, to examine whether the primary outcomes and MRC scores are correlated, their correlations will be compared using Spearman rank correlations at 3 months and 6 months separately.

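### Section 6.0 judges whether fluorescence is accurate enough by its correlation with confocal, which cannot show agreement, and this is not reconciled with the equivalence comparison in Section 10.0

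*Protocol*

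**What the plan says.** Section 6.0 (Study Procedures), in the microscopy paragraph, plans a confocal subset: "Confocal microscopy will be utilized in 3 patients at each site to confirm nodal measurements, myelinated fiber density, and confirm presence of segmental demyelination". The next sentence gives the purpose of the comparison and the statistic to be used: "Correlation of confocal measurements with florescence measurements will be evaluated to determine whether florescence is sufficient for accurate measurements". No coefficient or threshold is named. The same paragraph opens by taking sufficiency for granted for some structures: "Epifluorescence microscopy (Leica DM4000) will be sufficient for identifying and measuring Pan NaV-immunoreactive nodes of Ranvier".

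Section 10.0 (Statistical Considerations), under Aim 2, returns to the same comparison with a different method. Confocal and fluorescence outcome measures will be "compared to examine whether the measurements are similar using a random-effects model along with application of bioequivalence testing methodology". Correlation is not mentioned there for this purpose, and equivalence is not mentioned in Section 6.0.

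Two absolute figures in the segmental-demyelination paragraph of Section 6.0 depend on the level of the reading: "20% will be used as the cutoff for CIDP" and "given the standard deviation was 4.1% in the previous study, we would expect a change greater than 5% to be meaningful".

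**The concern.** Whether one method can stand in for another is a question about the difference between paired readings: its mean (bias) and its spread. Correlation discards the mean difference and any change of scale. A method that always reads low, always reads high, or reads a fixed fraction of the reference can correlate perfectly with it. As a test of accuracy, it is the wrong statistic at any sample size.

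The protocol does contain an analysis that addresses agreement, in Section 10.0. However, the sentence that says what will determine sufficiency is the one in Section 6.0, and it names correlation. The two can give opposite answers on the same data, because a uniform offset passes correlation and fails equivalence, and nothing says which prevails. At stake is whether this pilot passes a reading method on to later studies as validated when the check could not have exposed a level error.

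**Working it through.** The protocol gives no margin, threshold or sample-size figure for this comparison, so there is no stated figure to reproduce. The checks below show what each criterion can detect.

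**Inputs from the protocol:** 20% cutoff and 5-point meaningful change (Section 6.0); 25 fibers per biopsy (Section 10.0); confocal in 3 patients at each site, number of sites not stated (Section 6.0); biopsies at baseline, day 90 and day 180 (Appendix A).

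**Assumptions:** the example rates, the SD of paired differences, and the use of 5 points as an agreement margin.

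**1. What correlation sees.** Take confocal values of 8, 20 and 32% (illustrative).

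| Fluorescence reads | Values | Mean difference | Pearson r |
|---|---|---|---|
| 75% of confocal | 6, 15, 24 | -(2+5+8)/3 = -5 points | 1.00 |
| 50% of confocal | 4, 10, 16 | -(4+10+16)/3 = -10 points | 1.00 |
| 5 points low throughout | 3, 15, 27 | -5 points | 1.00 |
| 5 points high throughout | 13, 25, 37 | +5 points | 1.00 |

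**2. Why the level can matter.** With 25 fibers, 20% is 5 fibers (counting exactly 20% as positive). If the confocal rate is 24% and fluorescence reads three quarters of it, 0.75 x 24 = 18%. The binomial probability of at least 5 of 25 then falls from 0.75 to 0.48. For change over time, a constant offset cancels within a patient but a proportional one does not: at half value, an 8-point fall (assumed) reads as 4 points, below the 5-point change. In all these cases r is still 1.00.

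**3. What an agreement analysis sees.** A paired equivalence test was simulated (margin 5 points either way, one-sided 0.05, 200,000 runs). With a true 5-point under-reading it wrongly passed in 3.5% to 5.1% of runs. With no bias, the pass rates for one pair per patient were:

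| Pairs | SD of differences 2 | SD 4.1 | SD 5.8 |
|---|---|---|---|
| 3 | 75% | 21% | 9% |
| 6 | 99.9% | 65% | 26% |
| 9 | 100% | 91% | 53% |

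**4. Worst case for size: one site, one biopsy per patient, 3 pairs.**
- Under independence, P(r > 0.9) = [1 - (2/pi) asin(0.9)]/2 = 0.144. The two-sided 5% critical value of r is 0.997, and the Fisher-z interval is undefined because n - 3 = 0.
- The patient-level 90% CI half-width is t(0.95, 2 df)/sqrt(3) = 2.92/1.732 = 1.69 SD. To fit within 5 points even with zero observed bias, the paired SD must be below 5/1.69 = 2.96 points.

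**5. Pairing at fiber level** (clustering ignored, so these are optimistic). The half-width is 1.645 x sqrt(d/N), with d the share of discordant fibers.
- One biopsy each, N = 3 x 25 = 75: 4.2 points at d = 5%, 6.0 at d = 10%.
- Three biopsies each, N = 225: 2.5 points at d = 5%, 3.5 at d = 10%.

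**The case against.** The strongest reply is that Section 10.0 governs analysis and already plans an agreement method capable of detecting bias, so the Section 6.0 sentence is loose laboratory wording. Much of this stands. A reader might infer that the two sections contradict each other, or that the method check rests on correlation alone. The text supports neither: both analyses can be run on the same data, and correlation is not called the only criterion. What survives is that the only sentence saying what determines sufficiency names the wrong statistic and is not tied to Section 10.0.

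Other tempting inferences also go too far:

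- *The comparison has only 3 patients.* The text says "Confocal microscopy will be utilized in 3 patients at each site". Neither the number of sites nor the number of confocal biopsies per patient is given, so the figures for 3 pairs are a floor. Nor is it true that equivalence can hardly succeed: it passes in 75% of runs with 3 pairs if the paired SD is 2 points.
- *Fluorescence misses gaps.* No direction or size of bias is documented.
- *All primary counts come from fluorescence.* The fiber-count paragraph names no microscope.
- *Patients would be misclassified at the cutoff.* The 20% was set from the group's earlier control and diabetic readings. If those used the same imaging, a shared bias would partly cancel. The protocol does not say how they were read.

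The absence of a margin is not counted as an error, since a statistical analysis plan may supply it. A small confirmatory subset is also proportionate in a pilot without a power calculation.

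**Conclusion.** The point holds as an unreconciled and ill-chosen criterion, and it is minor. Correlation cannot establish that fluorescence is accurate: offsets of 5 points in either direction and readings at half value all give r = 1.00, whereas an equivalence test with a 5-point margin passes a true 5-point under-reading in about 5% of runs or fewer. That conclusion does not depend on the number of patients. The practical consequence cannot be sized from the documents, because neither the bias nor the paired SD is known; the fall from 0.75 to 0.48 at the cutoff is an example under assumed rates, on the further assumption that the historical readings did not share the bias. The 5-point margin is borrowed from the protocol's treatment-change figure and would need confirming as a margin for measurement agreement.

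**What to change.** In Section 6.0, replace the correlation criterion with a reference to the Section 10.0 comparison and say that this comparison decides. Specifically:

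- Read the same fibers by both methods.
- Report the mean paired difference in percent demyelinated, with a 90% CI, from a model with patient as a random effect.
- Give limits of agreement for nodal lengths.
- Keep correlation, if wanted, as a descriptive figure only.
- Judge the CI against a stated margin. The 5-point change is a candidate, to be confirmed by the investigators.
- Report a CI that crosses the margin as inconclusive.
- State how many sites and how many biopsies per patient enter the comparison.

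The change is to analysis wording, provided the same fibers can be identified in both sets of images; it needs no extra patients, biopsies or staining. The downside is that the result may be inconclusive, which is likely if only about 3 patients with one biopsy each are compared.

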The prevalence of CIDP is estimated to be between 1-9 cases per 100,000 (3, 4). However, diagnosis can be difficult and these numbers may be an underestimate of the true prevalence. Nerve conduction studies are specific but over 15 diagnostic criteria have been published in an effort to improve sensitivity (5). One of the possible sources of insensitivity can be low amplitudes which could reflect conduction block rather than axonal loss but cannot be discriminated on nerve conduction studies (6). CSF protein elevation is present in 90% of patients, but can be present in 50% of patients misdiagnosed as CIDP (7) Nerve biopsy is specific, but shows demyelination in only 50-66% of biopsies (8, 9). Teased fiber preparation is technically challenging and not performed routinely at all labs. In addition, none of these methods have proved useful for determining efficacy of treatments. Motor strength and disability scores are nonspecific but have been the primary endpoint measures used in CIDP studies. No tool currently exists for identifying demyelination in CIDP as either a diagnostic test or to assess treatment effect. This hypothesis-generating study will assess whether skin biopsy can discriminately identify demyelination in CIDP patients from healthy controls and other neuropathies such as diabetes mellitus. In addition, because skin biopsies can be repeated over time, this study will assess whether this biomarker is responsive to treatment, which has not been shown with any previous biomarker.

As mentioned, glabrous skin biopsy affords a method of pathological assessment of distal nerves which is minimally invasive and repeatable. Saporta et al published evidence of segmental demyelination in CIDP patients in skin biopsy using them as controls for an inherited neuropathy study (10). Segmental demyelination was observed in all four CIDP patients studied. We have used this method to demonstrate abnormalities in myelin and the node of Ranvier in diabetic subjects and healthy controls with average age of 53 (35-75). We observed 5% segmental demyelination in healthy controls and 7.3% in type 1 diabetic patients, 7.7% in type 2 diabetic patients (11). We propose to use this technique to study patients diagnosed with CIDP to evaluate its usefulness as a potential diagnostic tool and as a biomarker of treatment efficacy. We expect to observe a significantly higher percentage in CIDP than our previous diabetic

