Aim 1. We will obtain glabrous skin biopsies in 10 CIDP patients to demonstrate increased percentage of myelinated fibers with segmental demyelination using immune-histochemical labeling of myelin and axonal proteins compared to those of historical healthy control and diabetic subjects. We will demonstrate that this method will be able to discriminate CIDP patients from healthy controls and diabetic neuropathy patients.

Aim 2. We will perform follow up biopsies 3 months and 6 months after treatment to demonstrate whether there is decreased segmental demyelination after treatment.

Aim 3. We will compare measurement of segmental demyelination in vivo to medical research council (MRC) scores for muscle strength for each patient.

The overall goal is to provide preliminary data for a future study to demonstrate using SClg and IVIg is efficacious in preventing in vivo segmental demyelination and that this correlates with improvement in patient outcomes.

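### The Aim 2 outcomes are read only on surviving axons, so a falling demyelination score cannot by itself be told from selective loss of demyelinated fibers; the change in fiber density should be analysed beside it

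*Protocol*

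**What the plan says.** Section 6.0 (Analysis of segmental demyelination) defines the numerator of the score by "gaps of MBP stain within a fiber where MBP stain is visible on both sides of gap and PGP 9.5 stain is present". The denominator is the total number of fibers counted in that biopsy. Section 10.0 makes this a primary outcome as "the number of fibers with segmental demyelination (out of a random sample of 25 fibers", together with the average length of demyelinated segments and the number of fibers with sodium channels spread over denuded axons.

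Aim 2 in Section 2.0 plans biopsies after treatment "to demonstrate whether there is decreased segmental demyelination after treatment". In Section 10.0, "signed rank tests will be used to test whether there would be any improvement after treatment in the primary outcomes", at 3 and 6 months separately, each against baseline. Section 6.0 says of the size of effect that "we would expect a change greater than 5% to be meaningful". Under the infusion heading it states that each patient acts as his or her own control, and that the percentage is expected to fall with treatment.

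Myelinated fiber density and Meissner corpuscle density are listed biopsy measures in Section 6.0. The only test that Section 10.0 states for the wider morphometry compares CIDP patients with healthy controls from an earlier study.

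**The concern.** A fiber can leave the numerator in three ways. It can remyelinate, its axon can disappear, or the myelin on one side of the gap can disappear. Only the first is benefit. Each biopsy draws a new sample from the fibers then present, so a lost fiber is replaced by another and leaves no trace in the percentage.

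The other two primary outcomes do not protect against this. Sodium-channel spread is counted on denuded axons, so the count drops when those axons go. Segment length is measured only on fibers that remain.

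The study is meant to show whether the measure responds to treatment and to inform later, larger studies. Selective fiber loss would push the result towards the hypothesis, and there is no concurrent untreated group to expose it.

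**Working it through.** The protocol has no power calculation or stated effect to reproduce. The check concerns how the ratio behaves.

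**Inputs**
- From Section 6.0: the score definition, the 20% cutoff for CIDP, and 5 percentage points as a yardstick.
- From Section 10.0: 25 sampled fibers and 10 patients.
- Assumed: baseline scores of 20, 30 and 40% (no expected CIDP mean is given) and all rates of fiber loss (none is given).

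**Formula.** Let p be the baseline score, f the fraction of demyelinated fibers lost and g the fraction of intact fibers lost, with no remyelination and no new demyelination. Then

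new score = p(1−f) / [p(1−f) + (1−p)(1−g)].

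This is below p whenever f > g and equals p when f = g. With g = 0, a fall from p to q needs f = (p−q) / [p(1−q)], which is a share p·f of all fibers.

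**Loss needed for a 5-point fall (g = 0)**

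| Baseline p | f | Share of all fibers |
|---|---|---|
| 20% | 0.05/(0.20×0.85) = 29% | 5.9% |
| 30% | 0.05/(0.30×0.75) = 22% | 6.7% |
| 40% | 0.05/(0.40×0.65) = 19% | 7.7% |

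**Score after a given loss**

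| Baseline | f = 25%, g = 0 | f = 50%, g = 0 | f = 50%, g = 25% |
|---|---|---|---|
| 20% | 15.8% | 11.1% | 14.3% |
| 30% | 24.3% | 17.6% | 22.2% |
| 40% | 33.3% | 25.0% | 30.8% |

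**Signed rank test.** A simulation used 10 patients, 25 fibers per biopsy, the same f in every patient, g = 0 and no remyelination. Patient scores came from a beta distribution with parameters summing to 20, which is a further assumption. There were 2,000 trials per setting, tested two-sided at 5%. A significant decrease appeared in about 2% of trials with no loss, 19 to 27% with a quarter of demyelinated fibers lost, and 64 to 86% with half lost, across the three baselines.

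**Loss of flanking myelin.** If the fiber stays in the denominator but no longer has MBP on both sides of the gap, a 5-point fall needs a fraction 0.05/p of demyelinated fibers to do so: 25%, 17% and 12.5% at the three baselines.

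**What density adds.** Take 100 fibers in a fixed area, 20 of them demyelinated.
- Ten remyelinate: the score is 10/100 = 10%, intact fibers go from 80 to 90, and the total stays at 100.
- Ten are lost: the score is 10/90 = 11.1%, intact fibers stay at 80, and the total falls to 90.

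The percentages are almost the same, while the densities separate the two cases. This assumes that fibers with a gap are included in the density count.

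**The case against.** The definition itself is sound. A gap with myelin on both sides and a preserved axon is what makes the lesson segmental demyelination rather than axonal loss, and the score measures what Aim 2 asks about. That stands; the point concerns how a fall is interpreted.

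A reader might infer that the background text concedes progressive axonal loss in CIDP, because it mentions "low amplitudes which could reflect conduction block rather than axonal loss". It does not. That sentence explains why nerve conduction studies are insensitive, and no part of the protocol says that demyelinated fibers go on to lose their axons, or how fast.

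A reader might also infer that a deteriorating patient would be counted as a treatment response. There is no responder rule. Aim 2 is a group-level test, and the 5% figure is an expectation placed beside a statement that treatment effects are unknown.

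The illustration is favourable to the concern. A fifth to nearly a third of demyelinated fibers must vanish within 6 months, with no intact-fiber loss, and new demyelination in a progressing patient would raise the score.

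Finally, the protocol does collect other evidence: density, MRC and INCAT at each biopsy visit, and repeat nerve conduction at Day 180. Patients with escalating weakness who try additional treatments are released, which removes some of the patients at issue. However, no stated rule links these measures to the reading of Aim 2. The Aim 3 correlations with MRC are taken across patients at each visit, not on changes within patients.

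**Conclusion.** The point holds as a gap in interpretation, not as a demonstrated bias. All three primary outcomes depend on surviving axons, so a fall in the percentage is ambiguous between remyelination and selective loss of demyelinated fibers, and the Aim 2 analysis as written cannot separate them. The size is unknown because the protocol gives no loss rate. The figure of about 6 to 8% of all fibers for a 5-point fall rests on loss confined to demyelinated fibers and on no new demyelination; equal loss has no effect. The stronger reading, that a fall would probably reflect fiber loss, is not supported. The study is a hypothesis-generating pilot, but its results are meant to feed later studies, and the measurement that would reduce the ambiguity is already being taken. The change is therefore worth making.

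**What to change.** In Section 10.0, Aim 2:
- Add the change from baseline at 3 and 6 months in myelinated fiber density, in demyelinated fibers per mm² (percentage × density) and in intact fibers per mm² (the remainder). Use the same signed rank tests, and report estimates and intervals beside the percentage.
- State that a group-level fall in the percentage is read as remyelination only if neither total nor intact-fiber density is also falling, and that it is considered together with the change in MRC and INCAT. Total density is needed because pure loss of demyelinated fibers leaves intact density flat.
- Judge density by its estimate and interval. A non-significant fall in 10 patients does not show that density was maintained.
- Tally PGP 9.5-positive fibers with MBP on only one side of the gap as a separate category, so that they are not absorbed into the intact group.
- Report internodal length only where confocal images exist, since Section 6.0 plans confocal microscopy in 3 patients per site.

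A per-patient label for possible fiber loss is not advised. Without a threshold, measurement noise alone would trigger it in about half of patients whose density is truly stable.

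The cost is a little more analysis and one extra tally on sections already stained, with no added biopsy or visit. The protocol gives no variability for density, and with 10 patients the changes will be imprecise, so some apparent improvement may remain indeterminate.
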